### **9.8.1 Adverse Events**

Adverse events will be coded using the Medical Dictionary for Regulatory Activities (MedDRA) coding dictionary. Treatment-emergent AEs will be defined as any event with a start date occurring on or after first dose of study medication.

The incidence of treatment-emergent AEs will be summarized by body system, preferred term, and treatment group. If a subject reports the same AE more than once, then that subject will be counted only once for the summary of that AE, using the most severe intensity or highest relationship to study medication.

Treatment-emergent AEs will be summarized as follows:

- All treatment-emergent AEs;
- All treatment-emergent AEs by intensity;
- All treatment-emergent AEs by relationship to study drug;
- All treatment-emergent SAEs; and
- All treatment-emergent AEs that led to premature discontinuation from study.

### **9.8.2 Clinical Laboratory Assessments**

Hematology, blood chemistry, and urinalysis parameters will be summarized at Baseline and at Visit 7, as well as changes from Baseline to Visit 7. Laboratory values and changes from Baseline in laboratory values will be summarized descriptively overall and by treatment group.

A summary of shifts from Baseline to final evaluation will be provided for each treatment group for each parameter. The normal range for each parameter will be used to create categories of low, normal, or high. Any result higher than the ULN or lower than the LLN will be categorized as high or low respectively, and any result within the lower and upper limits of normal will be categorized as normal. The number and percentage of subjects in each treatment group in each shift category from Baseline to final evaluation will be shown for each parameter.

### **9.8.3 Vital Signs and ECGs**

Vital sign measurements will be summarized at Baseline and at each study visit. In addition, changes from Baseline to each study visit in vital sign and ECG measurements will be summarized.

ECG measurements will be summarized at Baseline and at Visit 7. In addition, changes from Baseline to Visit 7 in vital sign and ECG measurements will be summarized.

The incidence of sponsor-defined, potentially clinically significant, post-treatment vital sign values will also be presented by treatment group.

### **9.8.4 Other Safety Variables**

Concomitant medications taken during study will be categorized by World Health Organization (WHO) classification for therapeutic class and drug name and summarized by number and percentage of subjects by treatment group. Prior medications will also be summarized.

C-SSRS data will be listed.

## **10 ETHICS, LEGAL, AND ADMINISTRATIVE ASPECTS**

### **10.1 Institutional Review Board**

The Principal Investigator will provide the IRB with all requisite materials, including a copy of the protocol, ICF, and any subject information or advertising materials. The study will not be initiated until the IRB provides written approval of the protocol and the ICF and until approved documents have been obtained by the Principal Investigator and copies received by the Sponsor's designee. All amendments will be sent to the IRB for information (minor amendment) or for submission (major amendment) before implementation. The Principal Investigator will supply the IRB and the Sponsor's designee with appropriate reports on the progress of this study, including any necessary safety updates, in accordance

with the applicable government regulations and in agreement with policies established by the Sponsor.

## **10.2 Ethical Conduct of the Study**

The study will be performed in accordance with Health Insurance Portability and Accountability Act (HIPAA) regulations, FDA GCP Regulations (21 Code of Federal Regulations parts 50, 56, and 312) and International Conference on Harmonisation (ICH) guidelines for GCP (E6) and clinical safety data management (E2A).

## **10.3 Subject Information and Informed Consent**

In compliance with GCP guidelines, all subjects will be informed of the purpose of the research, possible risks of participation, and their rights to withdraw at any time from the study without prejudice and without jeopardy to the subject's future medical care at the center. Each subject must give informed written acknowledgment (signed ICF) to the Investigator prior to participation in the study. Each subject residing in the US must also provide HIPAA authorization. Each subject will be given a copy of their signed ICF.

No subject is to participate in study activities until written informed consent has been obtained. Documentation of the informed consent process and subject information discussion must appear in the subject's medical record, and include a statement that informed consent was obtained prior to participation in the study. Signed ICF acknowledgments must remain in the subject's file and be available for verification by monitors, auditors, and/or inspectors at any time.

## 11 APPENDICES

### 11.1 Appendix A

#### Listing of Laboratory Assays

Serum chemistry panel:	Hematology complete blood count:
Alanine aminotransferase (ALT)	White blood cell count (WBC)
Albumin	Red blood cell count (RBC)
Alkaline phosphatase	Hemoglobin
Aspartate aminotransferase (AST)	Hematocrit (packed cell volume)
Bicarbonate	Mean cell volume (MCV)
Bilirubin (total)	Mean cell hemoglobin (MCH)
Blood urea nitrogen (BUN)	Mean cell hemoglobin concentration (MCHC)
Calcium	Platelet count
Chloride	Differential WBC
Creatinine	
Glucose (non-fasting)	
Potassium	
Sodium	
Total protein	
Uric acid	
Other:	
Thyroid-stimulating hormone (TSH)	
Serum pregnancy test (females of child-bearing potential)	
Urine dipstick pregnancy test (onsite)	
Drugs of abuse screen (urine onsite)	
Blood alcohol level	
Glycosylated hemoglobin (HgA1C)	
Hepatitis C virus RNA (for subjects who report positive history of HCV infection that is now completely treated)	
CYP 2D6 (only samples from randomized subjects who opt in will be analyzed)	
Population pharmacokinetic samples	

## 11.2 Appendix B

### Prohibited Concomitant Medications

Subjects are not to use an investigational medication from another trial during the study or for the 60 days prior to study start. Prohibited concomitant medications can be resumed after Visit 8.

Sedative hypnotics are excluded unless they have been on a stable dose at least one month prior to screening and will be continuing their use during the study.

The table below shows examples of prohibited concomitant medication classes that are not allowed in the study; the list is not intended to be comprehensive. Some of the example medications listed are included more than once.

Prohibited Medication Class	Examples
Any stimulant used for any indication or non-stimulant medications for ADHD	Stimulants: methylphenidate, dexmethylphenidate, amphetamine, dextroamphetamine, lisdexamfetamine Non-stimulants: amoxetine, guanfacine, clonidine, bupropion
Monoamine oxidase inhibitors	selegiline, isocarboxazid, phenelzine, tranylcypromine
Serotonergic drugs	SSRIs, SNRIs, triptans, tricyclic antidepressants, fentanyl, lithium, tramadol, tryptophan, buspirone, St. John's wort
Mood stabilizers	lithium, valproate, quetiapine
Anticonvulsants	phenobarbital, phenytoin, primidone
Anticoagulants	warfarin
Antipsychotics	risperidone, olanzapine, haloperidol
Tricyclic antidepressants	desipramine, protriptyline
Medications with pressor effects	phenylephrine, pseudoephedrine, ephedrine, midodrine, fludrocortisone
Systemic corticosteroids	prednisone, methylprednisolone, dexamethasone

Psychotropic medications or those with psychotropic properties (some are already noted above)	Antidepressants, antipsychotics, mood stabilizers, antianxiety agents, certain non-prescription cold allergy medications (e.g., diphenhydramine, dextromethorphan)
Acidifying agents	Gastrointestinal acidifying agents (e.g., glutamic acid HCl, ascorbic acid)  Urinary acidifying agents (e.g., ammonium chloride, sodium acid phosphate, methenamine salts)
Alkalinating agents	Gastrointestinal alkalinating agents (e.g., sodium bicarbonate)  Urinary alkalinating agents (e.g., acetazolamide)
CYP 2D6 inhibitors	paroxetine, fluoxetine, quinidine, ritonavir
Other medications	halogenated anesthetics, phenylbutazone, chlorpromazine, ethosuximide

ADHD = attention deficit hyperactivity disorder; CYP = cytochrome P450; SNRI = serotonin-norepinephrine reuptake inhibitor; SSRI = selective serotonin reuptake inhibitor

1. PURPOSE OF THE STATISTICAL ANALYSES

The purpose of the analyses described in this document is to compare the safety and effectiveness of AR19 (Amphetamine Sulfate) compared to placebo in adult subjects with Attention Deficit Hyperactivity Disorder (ADHD).

The statistical analysis plan (SAP) is written with due consideration of the recommendations outlined in the most recent International Conference on Harmonization (ICH) E9 Guideline entitled Guidance for Industry: Statistical Principles for Clinical Trials [1] and the most recent ICH E3 Guideline, entitled Guidance for Industry: Structure and Content of Clinical Study Reports [2].

2. PROTOCOL SUMMARY

2.1 Introduction

Attention deficit hyperactivity disorder (ADHD) is a neurobehavioral disorder which typically presents in childhood. As defined in the Diagnostic and Statistical Manual of Mental Disorders, Fifth Edition (DSM-5™), ADHD is characterized by pervasive and impairing symptoms of inattention, hyperactivity, and impulsivity which begin in childhood. ADHD often persists into adulthood with one-half to two-thirds of child patients continuing to be symptomatic adults. The estimated prevalence of ADHD in adults in the United States is 4.4%. ADHD causes significant impairment in patients throughout the lifespan. Adults with ADHD are more likely to quit a job or be fired, have auto accidents, experience sudden changes in personal or career goals, and have higher perceived social and emotional stress.

Specific etiology of this disorder is unknown, and there is no single diagnostic test. It is apparent that the prefrontal cortex (PFC) plays a significant role in maintaining executive function, and that patients with ADHD appear to have less-than-adequate PFC activity, resulting in an overall inability to regulate impulsive behavior. Adequate diagnosis requires the use not only of medical but also of special psychological, educational, and social resources. Learning may or may not be impaired. The diagnosis must be based upon a complete history and evaluation of the patient and not solely on the presence of the required number of DSM-5™ characteristics.

The core symptoms used to diagnose ADHD in adults are inattention and hyperactivity-impulsivity. It has, however, been recognized for decades that many adult ADHD patients experience clinically significant levels of emotional dysregulation. Items pertaining to emotional dysregulation are contained in certain domains of several existing tools, including the Behavior Rating Inventory of Executive Function—Adult Version (BRIEF-A), Difficulties in Emotion Regulation Scale (DERS), and Affective Style Questionnaire (ASQ).

Controlled clinical trials have consistently demonstrated that stimulants (amphetamine and methylphenidate) substantially reduce the characteristic symptoms and functional impairment of patients with ADHD. Stimulants have a large effect size, with a mean of 0.73 to 0.96 in placebo-controlled adult ADHD trials.

Amphetamine and methylphenidate both contain chiral centers that give rise to distinct enantiomeric forms. Amphetamine, in particular, exists as dextro- and levo-amphetamine isomers that have different pharmacokinetic and neuropharmacological properties. Several products have been marketed containing different proportions of each isomer. Dexedrine, for example, consists of pure d-amphetamine; while mixed amphetamine salts such as Adderall consist of a ratio of approximately 3:1 d-amphetamine to l amphetamine. Benzedrine, a product first marketed in 1933, consisted of a racemic mixture of approximately 50% d-amphetamine and 50% l-amphetamine.

██████████ is a marketed immediate-release (IR) formulation of amphetamine sulfate indicated for narcolepsy, ADHD, and exogenous obesity. Amphetamine is a sympathomimetic amine with central nervous system (CNS) stimulant activity and is a 1:1 racemic mix of d-amphetamine and l-amphetamine. The l-isomer is more potent than the d isomer in cardiovascular activity but less potent in causing CNS excitatory effects.

In response to the growing misuse of amphetamines, including by intranasal administration, AR19 is an abuse-deterrent formulation of a 1:1 racemic mixture of d- to l amphetamine sulfate. Enhancements to the current IR formulation of ██████████ are intended to achieve a level of deterrence against abuse when the formulation is manipulated and administered by unintended routes (e.g., intranasal, intravenous). The abuse-deterrent capabilities of AR19 are attributed to pellets within the capsule that confer abuse-deterrent properties.

Results of a recent PK study verified that AR19 is bioequivalent to currently marketed ██████████.

Racemic amphetamine was the first stimulant studied for treatment of behavioral disorders in children in 1937. However, only one study has been conducted to date documenting the efficacy of a 50% d-amphetamine and 50% l-amphetamine compound (██████████) in the treatment of ADHD.

This study was conducted in children ages 6 to 12 years and demonstrated efficacy beginning at 45 minutes and continuing through 10 hours after administration of a single dose. No studies evaluating the effects of this mixture of d:l amphetamine have been completed in adults. The current study will test the safety and efficacy of this

composition (AR19) in adult subjects 18 through 55 years old with ADHD.

2.2 Study Objectives

The primary objective of this study is to assess the efficacy of AR19 compared to placebo using the Adult ADHD Investigator Rating Scale (AISRS).

2.3 Overall Study Design and Plan

This randomized, fixed-dose, double-blind, multi-center trial investigates the safety and efficacy of AR19 in the treatment of ADHD in adults from 18 through 55 years of age.

Safety parameters and therapeutic effect will be evaluated throughout the trial.

Subjects will be randomized to 20 or 40 mg AR19 daily or placebo in a 1:1:1 ratio in this fixed dose study. The expected drop-out rate is projected at 20%.

The study will consist of:

- A 30-day Screening period and Baseline evaluation
- Titration with AR19 for 4 weeks to 20 or 40 mg daily dose or placebo
- At least two weeks at a stable dose of AR19 or placebo
- Post Withdrawal Follow-Up phone call at Visit 8

Study visits will be conducted according to the Schedule of Events (Appendix 14.1).

Subjects who have signed an informed consent form (ICF) and who satisfy the inclusion/exclusion criteria will receive study drug twice daily, once in the morning and again four to six hours later. Study medication dosing will start at 10 mg/day and will be titrated in weekly intervals in 10-mg increments to 20 or 40 mg/day, depending on randomization.

It is anticipated that approximately 30 sites will participate in the study. Subject enrollment will continue until approximately 312 subjects are enrolled.

2.4 Study Population

Approximately 312 adult subjects (male or female) with a diagnosis of ADHD per DSM-5™ criteria will be enrolled. Subjects must be 18 to 55 years old, inclusive, at the time of Screening.

2.5 Method of Assigning Subjects to Treatment

Subjects who satisfy the inclusion/exclusion criteria will undergo a 7-day washout of previous ADHD stimulant medications, and AR19 or placebo will then be initiated at 10 mg/day the morning after Visit 2. Depending on treatment group, the daily dose will be increased in 10-mg increments every week to 20 or 40 mg/day. The study duration from first dose of study drug to the follow-up visit is expected to be approximately 6 weeks.

Subjects will be monitored for safety and for therapeutic response to AR19 treatment. Safety and clinical response assessments will be performed at each visit or more frequently if clinically indicated.

Each subject must meet all the inclusion criteria and none of the exclusion criteria to be eligible for enrollment in the study. Waivers to inclusion/exclusion criteria will NOT be granted.

Randomization will occur via Interactive Web Response System (IWRs) at Visit 2, if a subject meets all inclusion and no exclusion criteria. Subjects will be randomized 1:1:1 to placebo or 20 or 40 mg AR19/day. Randomization will take place according to a fixed schedule using a permuted block design with no stratification by clinical site.

2.6 Treatment Regimens

The following dosing procedures will be followed:

- The dosing regimen will be two capsules twice daily. All subjects will be instructed to take their first dose (two different colored capsules) of study medication in the morning. The second dose (two different colored capsules) should be taken four to six hours later.
- Study medication will be administered orally by swallowing the capsules.
- Study drug can be taken with or without food.

This study is a fixed dose regimen. Dose adjustments are not allowed during the study.

After Screening and Baseline evaluations are complete, eligible subjects will be randomized 1:1:1 to one of two fixed-dose groups (AR19 10 mg p.o. b.i.d. or AR19 20 mg p.o. b.i.d.) or placebo.

Subjects unable to tolerate their AR19 dose at any time during study drug administration will be withdrawn from the trial.

Subjects will begin dosing with double-blind study drug the morning following the Baseline visit. The first dose will be taken in the morning (2 capsules) and the second dose (2 capsules) will be taken 4 to 6 hours later.

Table 2.6.1 Titration Scheme for 20 mg Daily Dose

Kit Assigned on Visit/Day	First Dose		Second Dose	
Visit 2, Day 1	20 mg Placebo	10 mg	20 mg Placebo	10 mg Placebo
Visit 3, Day 8	20 mg Placebo	10 mg	20 mg Placebo	10 mg
Visit 4, Day 15	20 mg Placebo	10 mg	20 mg Placebo	10 mg
Visit 5, Day 22	20 mg Placebo	10 mg	20 mg Placebo	10 mg
Visit 6, Day 29	20 mg Placebo	10 mg	20 mg Placebo	10 mg

Table 2.6.2 Titration Scheme for 40 mg Daily Dose

Kit Assigned on Visit/Day	First Dose		Second Dose	
Visit 2, Day 1	20 mg Placebo	10 mg	20 mg Placebo	10 mg Placebo
Visit 3, Day 8	20 mg Placebo	10 mg	20 mg Placebo	10 mg
Visit 4, Day 15	20 mg	10 mg Placebo	20 mg Placebo	10 mg
Visit 5, Day 22	20 mg	10 mg Placebo	20 mg	10 mg Placebo
Visit 6, Day 29	20 mg	10 mg Placebo	20 mg	10 mg Placebo

Subjects randomized to placebo will receive the 10 mg and 20 mg placebo capsules for the first and second dose (4 capsules/day) during the trial.

2.7 Sample Size Determination

The primary efficacy endpoint is change from Baseline in AISRS total score at Visit 7 (Week 5). A Bonferroni adjustment will be utilized for the primary efficacy analysis where each AR19 dose will be tested against placebo separately using an alpha of 0.025 for each test.

Eighty-seven (87) subjects per treatment group will provide approximately 90% power to detect a 7.0-point difference in mean change from Baseline to Visit 7 in the AISRS total score between one of the AR19 doses and placebo with a standard deviation of 13.0 and Type I error of 0.025 using a two-sample test. To account for an approximate 20% dropout rate, a total of 104 subjects will be randomized to each of the three treatment groups for a total of 312 randomized subjects.

3. GENERAL ANALYSIS, REPORTING, AND PROGRAMMING CONVENTIONS

This section discusses general policies to be employed in the analysis and reporting of the data from the study. Departures from these general policies may be given in the specific detailed sections of this SAP. When this situation occurs, the rules set forth in the specific section take precedence over the general policies.

Descriptive statistics for continuous parameters will include number of observations (n), mean, median, standard deviation, minimum, and maximum values. Descriptive statistics for categorical parameters will include frequency counts and percentages. All study data will be listed by subject, treatment group, sequence (as applicable), and time point (as applicable).

Hypothesis testing, unless otherwise indicated, will be two-sided and performed at the 2.5% significance level. When confidence intervals are presented, they will be two-sided with a confidence coefficient of 97.5%. P-values will be reported to 3 decimal places if greater than 0.001. If less than 0.001, report '<0.001'. P-values and significant levels will be reported as 0.025 rather than .025.

Data will be summarized based on the recorded visit; no visit windowing will be performed.

No preliminary rounding will be performed; rounding will only occur after analysis. To round, the digit to right of last significant digit will be considered: if < 5 then round down, if ≥ 5 then round up. Means and medians will be presented with one more decimal place than the precision of the data. Standard deviations will be presented with two more decimal places than the precision of the data. Percentages will be presented with one decimal place. Minimums and maximums will be presented with the same precision as the original data.

All analyses will be performed using the SAS System® version 9.3 or higher.

The following general programming conventions will apply:

Exposure Days: (Last dosing date – first dosing date + 1)

Compliance: [(Number of doses taken)/(number of doses planned)]*100

Duration days: (End/resolution date – start/onset date +1)

Study day: (Date of interest – first dosing date +1) if date of interest is on or after the first dosing date: (Date of interest – first dosing date) if date of interest is before the first dosing date.

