**Blood and urine samples MUST be drawn after efficacy and safety assessments are completed.**

#### **6.1.5 Early Termination**

Every effort should be made to have subjects who withdraw early from the trial return to the site to complete an Early Termination Visit and return any unused study drug.

The following activities should be performed:

- Blood pressure and pulse (in triplicate via automated machine)
- Body weight
- Physical examination
- Resting 12-lead ECG
- Laboratory tests
  - Serum chemistry panel
  - Hematology
  - Urinalysis
  - Urine pregnancy test for females of child-bearing potential
- AISRS
- BRIEF-A
- DERS
- ASQ
- CGI-S
- CGI-I
- Follow-up C-SSRS
- AE assessment
- Concomitant medications assessment
- eCRF entry for early withdrawal
- Study drug accountability

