7.1.2 Assessment Time Windows

Data will be summarized based on the recorded visit; no visit windowing will be conducted. Visit 7 must be performed as scheduled based on the protocol, allowing for consistent and reliable efficacy measurements.

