7.4 Analysis Methods

7.4.1 Primary Efficacy Analyses – AISRS Total Scores

The primary efficacy analysis will be performed on the FAS population. The primary efficacy outcome is the change from baseline in AISRS total score at Visit 7 (Week 5) in AR19 (20 and 40 mg/day) versus placebo. To account for these comparisons, a Bonferroni multiple comparison adjustment will be utilized. Both comparisons will be conducted at the 0.025 (0.05/2) alpha level. No other adjustments for multiplicity will be applied to any other endpoints or comparisons. Change from Baseline in AISRS at Visit 7 will be compared between each of the two different AR19 dose groups and the placebo group.

The key elements of the primary efficacy analysis are as follows:

Data: AISRS total scores measured at Baseline through Visit 7. All available data will be used; there will be no imputation of missing data.

Model: Restricted maximum likelihood (REML)-based MMRM analysis

Fixed effects: The following fixed effects are planned:

- Treatment (class effect: AR19 20 mg/day, AR19 40 mg/day, placebo)
- Week (class effect: Weeks 1, 2, 3, 4, 5)
- Baseline AISRS total score
- Treatment-by-week interaction

Residual Variance-Covariance Matrix: An unstructured correlation matrix will be used to model the within-patient errors and restricted maximum likelihood estimation will be used. The Kenward-Roger method will be used for the denominator degrees of freedom. Should the model fail to converge with an unstructured covariance matrix, alternative covariance structures will be applied, in the following order, until the model converges: heterogeneous Toeplitz, heterogeneous compound symmetry, then heterogeneous autoregressive(1).

The null hypothesis:

H_0 : Change from baseline AISRS total scores at Visit 7 are the same for AR19 and placebo

will be tested against the two-sided alternative hypothesis

H_1 : Change from baseline AISRS totals scores at Visit 7 are not the same for AR19 and placebo.

Within this model, pairwise comparisons (using least squares [LS] mean contrasts) will be made to compare AISRS at Visit 7 for each AR19 dose level with placebo separately (primary efficacy outcome). Treatments will also be compared at other weeks as secondary analyses. If differences between baseline characteristics exist between the three treatment groups in this comparison, it will be investigated whether adjustment for these characteristics is clinically relevant and necessary as a sensitivity analysis.

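### Early Termination AISRS and CGI ratings have no assigned week, so on a literal reading of the SAP they stay out of the Weeks 1–5 primary model

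*SAP*

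**What the plan says.** Protocol Table 6.1.1 and SAP Appendix 14.1 give Early Termination its own column, with no visit number, study day or week. AISRS, CGI-S and CGI-I are marked in it. Protocol 6.1.5 asks sites to obtain the visit: "Every effort should be made to have subjects who withdraw early from the trial return to the site to complete an Early Termination Visit". Protocol 4.3 adds that the procedures are done where possible.

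SAP 3 states: "Data will be summarized based on the recorded visit; no visit windowing will be performed". Specific sections override that general one, but SAP 7.1.2, the efficacy section on time windows, repeats that "no visit windowing will be conducted" and makes no exception for ET.

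SAP 7.4.1 takes AISRS totals from Baseline to Visit 7 and lists the time effect as "Week (class effect: Weeks 1, 2, 3, 4, 5". The same section says "All available data will be used; there will be no imputation of missing data". SAP 7.1.1.2 says the model includes every dosed subject with at least one on-treatment post-baseline rating, and SAP 4.1.2 defines the FAS in the same way. No section assigns an ET rating to a week.

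**The concern.** These statements cannot all be followed. A score recorded under Early Termination has no level of the week factor, so it has no row in the model. A subject whose only post-baseline AISRS is an on-treatment ET rating is in the FAS and is promised a place in the model, yet contributes nothing to it. The programmer would have to choose between two different primary analyses.

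The choice can matter. The MMRM relies on data being missing at random given the scores it uses. If subjects leave because of how they are doing on the day they leave, the ET rating is the score that records this. If that happens to a different degree in each arm, leaving the rating out can shift the Visit 7 contrast. Different routes out are plausible here: doses are fixed and subjects who cannot tolerate AR19 are withdrawn (Protocol 5.3, 5.6), while lack of effect may weigh more on placebo. That is an inference; the documents give no withdrawal reasons by arm.

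**Working it through.** **Plan's own figure.** SAP 2.7: "Eighty-seven (87) subjects per treatment group will provide approximately 90% power to detect a 7.0-point difference", with SD 13.0. SAP 7.4.1: "Both comparisons will be conducted at the 0.025 (0.05/2) alpha level", and the null "will be tested against the two-sided alternative hypothesis".

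n per arm = 2(z₀.₉₈₇₅ + z₀.₉₀)²σ²/δ² = 2 × (2.2414 + 1.2816)² × 13²/7² = 85.6, so 86. The two-sample t test with 87 per arm has power 0.9004. The figure reproduces.

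**Ratings at stake.** 0.20 × 104 = 20.8 per arm, about 21; 0.20 × 312 = 62.4 overall, about 62. These are upper limits, because not every withdrawal will have an ET rating.

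**Bias if ET ratings are left out.** The documents give no figure, so this part rests on assumptions.

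- One dose against placebo, 200,000 per arm. Mean changes at Weeks 1–5: placebo −2, −3, −4, −5, −5; active −4, −7, −10, −11.5, −12. True Week 5 difference −7.0.
- SD 13 at each week; AR(1) or compound-symmetry correlation of 0.5, 0.7 or 0.85.
- 20% dropout per arm. Where withdrawal is score-driven, logit P(withdraw at week w) = b₀ ± 0.12 × (score at w − arm mean at w), with b₀ set to give 20%.
- Every withdrawal has an ET rating, taken in place of that week's visit.
- Week 5 contrast by maximum likelihood for monotone missing data, with unstructured covariance pooled over arms and no baseline covariate.

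Bias = estimate − (−7.0), range over the six correlation settings. A positive value understates the effect.

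| Withdrawal driven by exit score | ET left out | ET kept as that week |
|---|---|---|
| Neither arm | −0.10 to +0.03 | −0.10 to +0.03 |
| Both arms equally | −0.11 to +0.08 | −0.09 to +0.07 |
| Placebo only, poor responders leave | +1.15 to +1.28 | −0.02 to +0.07 |
| Active only, poor responders leave | −1.27 to −1.07 | −0.11 to +0.03 |
| Poor responders leave placebo, good responders leave active (extreme) | +2.24 to +2.65 | −0.07 to +0.07 |

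The simulation standard error is about 13 × √(2/200,000) = 0.04, so values up to about 0.1 are read as zero. For one-arm dependence, 1.07/7 = 15% and 1.28/7 = 18% of the assumed effect.

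**Low end of the range.** A simulation at trial size (104 per arm, SD 8 rising to 12.5, AR(1) 0.7, about 220 replicates, placebo-only dependence) gave estimated effects of 6.0 (strong dependence) and 6.5 (moderate) without ET ratings, against 6.9 with them: 6.9 − 6.0 = 0.9 and 6.9 − 6.5 = 0.4. Simulation error per estimate is about 12.5 × √(2/104)/√220 = 0.12, so 0.4 is approximate.

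**Subjects with no other rating.** In the large simulation, 4.4% to 5.4% of subjects left at the first post-baseline week, or about 5 to 6 of 104 per arm. This depends on the assumed timing of dropout.

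**The case against.** A reader might infer that the SAP discards the last score of every early withdrawal and that the primary contrast is therefore biased. The documents do not support that.

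- No section says ET scores are discarded. SAP 7.4.1 and 7.1.1.2 point the other way, SAP 3 speaks of how data are summarized, and how the eCRF labels the visit is not given. This stands: the defect is an unresolved rule whose literal reading excludes the scores.
- Not every withdrawal will have an ET rating. Loss to follow-up is a listed reason for withdrawal (Protocol 4.3). Earlier weekly scores stay in the model, and the schedule caps the interval between visits at 9 days for Visits 3–6.
- The bias is conditional. It vanishes under two of the mechanisms examined, and its sign is not fixed.
- SAP 7.1.1.2 describes a placebo-based imputation and a tipping-point analysis for departures from missing at random. These address part of the harm, but they are optional and do not say whether an ET rating counts as observed.
- The estimand at the end of SAP 7.4.1 covers subjects who stay in the trial through blinded treatment. The bias above is measured against the Visit 7 difference for all subjects, which is what an MMRM under missing at random estimates, so the estimand wording needs attention too.
- Assigning every ET score to a week would also be wrong. A withdrawn subject may be off drug at ET, and Protocol 5.9.2 foresees new ADHD therapy once study drug has been stopped for at least 24 hours. An ET rating on Day 31 after Visit 6 on Day 29, moved to the next empty week, would become a Week 5 value 5 days before Day 36, although SAP 7.1.2 requires Visit 7 to be performed as scheduled.

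**Conclusion.** The point holds as an unresolved rule for the primary analysis that should be settled before unblinding. The stated rules leave obtained ET scores out of the model and conflict with two other statements in the SAP. At most about 21 of 104 subjects per arm are affected.

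The bias is about zero if withdrawal is unrelated to the exit score or equally related in all arms. It is roughly 0.4 to 1.3 points of the assumed 7 if withdrawal is score-driven in one arm only. Both signs appear in the large simulation; the 0.4 comes from the trial-size run, which covered placebo-only dependence. The extreme case of opposite mechanisms gives more, but nothing in the documents makes it likely.

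All these sizes depend on assumed dropout mechanisms, timing and complete ET attendance. The near-zero bias with ET scores kept is a best case, since it assumes every withdrawal is rated and every rating is used. A rule limited to on-treatment, on-schedule ratings would recover less.

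**What to change.** Before unblinding, amend SAP 3, 7.1.2 and 7.4.1:

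- Keep no windowing for scheduled visits. Assign each on-treatment ET AISRS, CGI-S and CGI-I score to a scheduled week by study day.
- Define on-treatment relative to the last dose, and exclude off-drug ratings from the assignment. SAP 8.4 has a 24-hour limit for adverse events after early termination; whether that suits efficacy ratings is for the sponsor to decide.
- Assign a score to Week 5 only if it falls within the Visit 7 window (Day 36 ±2, so Days 34–38).
- State what happens when the target week already has a scheduled score, and when a score fits no week. Day 33, for example, is 3 days from Week 5 and 4 from Week 4, but outside the Visit 7 window.
- Align the day count. SAP 3 counts from the first dose, which is Day 2 of the visit schedule, so schedule Day 36 is SAP study day 35.
- Run the analysis without ET scores as a sensitivity analysis, and say whether ET scores count as observed in the imputation analyses.
- Reconcile the estimand wording in SAP 7.4.1 with the analysis.
- State how ET ratings of BRIEF-A, DERS and ASQ are handled, since these are also collected there.

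The cost is a short SAP amendment, one derivation from dates the SAP already uses, and one extra model run. The downside is that some ET ratings will lie a few days from the nominal day of their week.
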